9. SUPPORTING DOCUMENTATION AND OPERATIONAL CONSIDERATIONS

9.1 REGULATORY, ETHICAL, AND STUDY OVERSIGHT CONSIDERATIONS

INSTITUTIONAL REVIEW BOARD AND MULTI-SITES

UAMS IRB will serve as the IRB of record for all multi-sites. (should the study expand to additional sites) UAMS will serve as the main site. The main site, specifically the UAMS CTO Regulatory Unit, will be responsible for submitting documents to the UAMS IRB on behalf of the multi-sites and communicating to the multi-sites information from the UAMS IRB.

Multi-sites are expected to vaccinate 27 participants per site. When this goal is reached, each site can request to increase their goal as long as the overall enrollment has not been met. Multi-sites will use OpenClinica to enter safety and clinical data. All research laboratory analysis will be performed at or by UAMS, and the results will be shared with multi-sites as needed.

INFORMED CONSENT PROCESS

CONSENT AND OTHER INFORMATIONAL DOCUMENTS PROVIDED TO SUBJECTS

Consent forms describing in detail the study intervention, study procedures, and risks are given to the subject and written documentation of informed consent is required prior to starting intervention/administering study intervention. Any revisions of the consent form will be provided to the subjects as deemed necessary by the IRB or Sponsor before any subsequent trial interventions take place, and all consent form documents will be kept in the subject's binder.

CONSENT PROCEDURES AND DOCUMENTATION

Consent forms will be Institutional Review Board (IRB)-approved and the potential subject will be asked to read and review the document. The investigator will explain the research study to the potential subject and answer any questions that may arise. A verbal explanation will be provided in terms suited to the potential subject's comprehension of the purposes, procedures, and potential risks of the study and of their rights as research subjects. Potential subjects will have the opportunity to carefully review the written consent form and ask questions prior to signing. The potential subject should have the opportunity to discuss the study with their family or surrogates or think about it prior to agreeing to participate.

If the potential subject agrees to participate, he/she will sign the informed consent document prior to any procedures being done specifically for the study. Potential subjects must be informed that participation is voluntary and that they may withdraw from the study at any time, without prejudice. A copy of the informed consent document will be given to subjects for their records. The informed consent process will be conducted and documented in the source document (including the date). The rights and welfare of the subjects will be protected by emphasizing to them that the quality of their medical care will not be adversely affected if they decline to participate in this study.

9.2 STUDY DISCONTINUATION AND CLOSURE

Subjects are free to withdraw from participation in the study at any time upon request.

An investigator may discontinue a subject's participation from vaccination or from the study for the following reasons:

- Pregnancy
- Significant study intervention non-compliance
- Any subject experiencing a vaccine-related toxicity
- Disease progression, and/or unrelated health condition which requires discontinuation of the study intervention
- Any reason that the investigator feels it is not in the subject's best interest to continue

The sponsor may decide to stop the study at any point, for any reason.

INDIVIDUAL SUBJECT STOPPING RULES

Subjects who experience injection-induced/related serious dose limiting toxicities should be removed from the study treatment (vaccine) but will continue with assessments per the study calendar, including collection of study labs. Injection-induced serious toxicity will be defined (using CTCAE Version 5.0) as:

- Grade II or higher allergic reactions. Grade II is defined as "Oral intervention indicated". Grade III is defined as "Bronchospasm; hospitalization indicated for clinical sequelae; intravenous intervention indicated".
- Grade II or higher autoimmune reactions/disorders. Grade II is defined as "evidence of autoimmune reaction involving a non-essential organ or function (e.g., hypothyroidism)". Grade III is defined as "autoimmune reactions involving major organ (e.g., colitis, anemia, myocarditis, kidney)".
- Any Grade III or higher event.

If a subject becomes pregnant during her participation in the study, a medical monitor will determine whether or not she should be removed from the study. Medical records will be requested to determine the health of the mother and child.

For all other circumstances, the local site PI may determine whether or not a subject needs to be removed from the study. In either case written notification, documenting the reason for study suspension or termination, will be provided to the study subject, Investigator, ORRA, and local regulatory authorities. If a subject withdraws or is withdrawn, they will be asked to complete the Early Termination Questionnaire. Withdrawn subjects will not be replaced.

STUDY STOPPING RULES

If at any point in the study, $\geq 10\%$ of subjects experience injection-related serious toxicity, the study enrollment and injections will be suspended. These activities can only re-start after notifying the applicable regulatory agencies and with a permission to resume from the Medical Monitor and Sponsor.

The study enrollment and injections will be suspended if any subject experiences vaccine-related Grade IV or higher AE. These activities can re-start only after notifying the applicable regulatory authorities and with a permission to resume from the Medical Monitor and Sponsor.

If the study is prematurely terminated or suspended, the UAMS PI will promptly inform study subjects, the IRB, and Sponsor and will provide the reason(s) for the termination or suspension. Study subjects will be contacted, as applicable, and be informed of changes to study visit schedule. If only suspended, the study may resume once all concerns have been addressed, and satisfy the Sponsor, IRB and/or the FDA.

EMERGENCY UNBLINDING

If a medical emergency necessitating the identity of the injection administered occurs, the local site PI or a local Sub-Investigator will notify the sponsor and UAMS PI. The UAMS PI will be available 24 hours, 7 days a week, and if the medical emergency occurs after hours the UAMS PI should be notified via the afterhours number listed on the protocol title page. After permission is given to unblind by the UAMS PI, local site pharmacy will identify the injection to the requesting investigator and Study Coordinator, and note any incidence in the Randomization book. UAMS PI will notify the medical monitor if necessary for further review.

LOST TO FOLLOW-UP

A subject will be considered lost to follow-up if he or she fails to return for two (2) consecutive scheduled visits and is unable to be contacted by the study site staff.

The following actions must be taken if a subject fails to return to the clinic for a required study visit:

- The site will attempt to contact the subject and reschedule the missed visit as soon as possible and counsel the subject on the importance of maintaining the assigned visit schedule and ascertain if the subject wishes to and/or should continue in the study.
- Before a subject is deemed lost to follow-up, the investigator or designee will make every effort to regain contact with the subject (where possible, 3 telephone calls and, if necessary, a certified letter to the subject's last known mailing address or local equivalent methods). These contact attempts will be documented in the subject's medical record or study file.
- Should the subject continue to be unreachable, he or she will be considered to have withdrawn from the study with a primary reason of lost to follow-up.

TRAVEL STIPENDS

Travel stipends will be available based on institutional guidelines

CONFIDENTIALITY AND PRIVACY

Subject confidentiality and privacy is strictly held in trust by the participating investigators, their staff, and the sponsor(s). This confidentiality is extended to cover testing of biological samples and genetic tests in addition to the clinical information relating to subjects. Therefore, the study protocol, documentation, data, and all other information generated will be held in strict confidence. No information concerning the study or the data will be released to any unauthorized third party without prior written approval of the sponsor.

All study related documents will be kept in accordance with local institutional practices.

All research activities will be conducted in as private a setting as possible.

The study monitor, other authorized representatives of the sponsor, representatives of the IRB, regulatory agencies or pharmaceutical company supplying study product may inspect all documents and records required to be maintained by the investigator, including but not limited to, medical records (office, clinic, or hospital) and pharmacy records for the subjects in this study. The clinical study site will permit access to such records.

The study subject's contact information will be securely stored at each clinical site for internal use during the study. At the end of the study, all records will continue to be kept in a secure location for as long a period as dictated by the reviewing IRB, Institutional policies, or sponsor requirements.

KEY ROLES AND STUDY GOVERNANCE

UAMS Principal Investigator (PI)	Medical Monitor
[name]	[name]
University of Arkansas for Medical Sciences	University of Arkansas for Medical Sciences
Winthrop P. Rockefeller Cancer Institute	Winthrop P. Rockefeller Cancer Institute
7th Floor	7th Floor
[name]	[name]
[name]	[name]

MONITORING

The UAMS and local PIs will have the overall responsibility for assuring safety and gathering the data for the study with assistance from the sub-investigators, and research staff, under the guidance of the Institutional Review Board (IRB) and the study Sponsor.

Clinical site monitoring for the main site, UAMS, is conducted by ORRA to ensure that the rights and well-being of human subjects are protected; that the trial data are accurate, complete, and verifiable from source documents; and that the trial is conducted in compliance with the currently approved protocol/amendment(s), ICH GCP, and applicable regulatory requirements.

Clinical site monitoring for the external multi-sites is conducted by Marshall and Associates to ensure that the rights and well-being of human subjects are protected; that the trial data are accurate, complete, and verifiable from source documents; and that the trial is conducted in compliance with the currently approved protocol/amendment(s), ICH GCP, and applicable regulatory requirements. Monitoring specialists from Marshall and Associates will conduct periodic on-site, comprehensive monitoring as determined by a protocol-specific monitoring plan provided by the Sponsor,

The designated medical monitor will serve as the medical monitor for all sites. Safety and clinical data reported by the external multi-sites to the main site will be reviewed by the UAMS PI. The UAMS PI will notify the medical monitor of any AEs that will require their medical expertise, oversight, and consultation to ensure the safety and integrity of the subjects throughout the trial from the initial design of the study to the final close-out. Such AEs would include, but not limited to, any dose-limiting toxicities and unintended pregnancies. The dose-limiting toxicities are defined as vaccine-related allergic and autoimmune AEs greater than grade 1 and any other AEs greater than grade 2.

QUALITY ASSURANCE AND QUALITY CONTROL

Following written Standard Operating Procedures (SOPs), the monitors will verify that the clinical trial is conducted and data are generated and biological specimens are collected, recorded, and reported in compliance with the protocol and all applicable regulatory requirements.

DATA HANDLING AND RECORD KEEPING

DATA COLLECTION AND MANAGEMENT RESPONSIBILITIES

The investigator shall maintain a list of appropriately qualified persons to whom he has delegated trial duties. All persons authorized to make entries and/or corrections on case report forms will be included on the Delegation of Authority form.

The investigator and study staff are responsible for maintaining a comprehensive and centralized filing system of all study-related documentation.

Hardcopies of the study visit worksheets will be provided for use as source document worksheets for recording data for each subject enrolled in the study. Data recorded in the electronic case report form (eCRF) derived from source documents should be consistent with the data recorded on the source documents.

Clinical data (including AEs, concomitant medications, and expected adverse reactions data) and clinical laboratory data will be collected.

PROTOCOL DEVIATIONS AND VIOLATIONS

A deviation is a study event that is not covered under the existing protocol and represents a failure to comply with the protocol.

A violation is an event clearly occurring outside of the approved research activity, which also represents a failure to comply with the protocol, e.g., enrollment of a subject that fails to meet inclusion or exclusion criteria. A protocol violation refers to more serious non-compliance, which more often leads to exclusion of subjects from eligibility analysis or their discontinuation from the study.

If the protocol deviation/protocol violation does not represent a significant alteration in the approved protocol and/or affect the safety or welfare of the subject, it will be reported to the UAMS IRB at the time of Continuing Review.

If the protocol deviation or protocol violation represents a significant alteration in the approved protocol and/or if it affects the safety or welfare of the subject, it must be reported to the UAMS IRB immediately.

Multi-sites may capture protocol deviations and violations source documentation within their electronic record system. Additionally, the main site will document protocol deviations and violations in RPRS and the external sites will document protocol deviations and violations on a provided Protocol Deviations and Violations Log to ensure that all information is captured uniformly across multi-sites.

PUBLICATION AND DATA SHARING POLICY

This study will be conducted in accordance with the following publication and data sharing policies and regulations:

- National Institutes of Health (NIH) Public Access Policy
- NIH Data Sharing Policy
- Policy on the Dissemination of NIH-Funded Clinical Trial Information
- Clinical Trials Registration and Results Information Submission rule

Results will be submitted for publication in peer-reviewed journals and/or presented at professional society meetings at national and international levels.

CONFLICT OF INTEREST POLICY

The study leadership in conjunction with the UAMS IRB has established policies and procedures for all study group members to disclose all conflicts of interest and will establish a mechanism for the management of all reported dualities of interest. This research study is designed to test a product invented by [name]. UAMS and [name] are entitled to a share of royalties received from the sale of this product. The financial value of this interest might be affected by the results of this study. This means that UAMS and [name] could gain or lose money depending on the results of this study.

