7.2 SAFETY ASSESSMENTS

As one of the primary endpoints of this study is safety, the monitoring of AEs will be diligently recorded and reviewed. In the clinical setting, subjects will report any AEs since their last visit and immediately following each vaccination. Additionally, vital signs will be taken pre- and post-vaccination to monitor for

fluctuations in these parameters. Vital signs will be taken and blood drawn (CBC with diff, Chem 7, and LFTs) regularly throughout the study.

ASSESSMENT OF ADVERSE EVENTS

A physician, or designee, will evaluate a subject's AEs based on the NCI CTCAE Version 5.0. A physician will assess whether or not a particular event is likely to be related to the study drug. For more details on event reporting, see Section 7.4.

MONITORING TOXICITY

Injection-induced/related serious toxicity will be defined (using CTCAE Version 5.0) as:

- Grade II or higher allergic reactions. Grade II is defined as "Oral intervention indicated". Grade III is defined as "Bronchospasm; hospitalization indicated for clinical sequelae; intravenous intervention indicated".
- Grade II or higher autoimmune reactions/disorders. Grade II is defined as "evidence of autoimmune reaction involving a non-essential organ or function (e.g., hypothyroidism)". Grade III is defined as "autoimmune reactions involving major organ (e.g., colitis, anemia, myocarditis, kidney)".
- Any Grade III or higher event.

Subjects who have any of the above dose-limiting toxicities will be treated and referred for additional care as indicated with systemic steroids, topical steroids, epinephrine or Benadryl. These subjects will no longer receive the vaccine but will continue with assessments per the study calendar, including collection of study labs.

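### Section 9.2 allows removal from the study, not only from injections, for vaccine-related toxicity of any grade, and no recurrence or adverse-event follow-up is stated after removal

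*Combined protocol and SAP*

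**What the plan says.** The opening list of Section 9.2 begins: "An investigator may discontinue a subject's participation from vaccination or from the study for the following reasons". One reason is "Any subject experiencing a vaccine-related toxicity", with no grade or seriousness condition.

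The Individual Subject Stopping Rules, later in 9.2, are narrower. Subjects with injection-related serious or dose-limiting toxicity "should be removed from the study treatment (vaccine) but will continue with assessments per the study calendar". Section 7.2 has the same rule for the same definition: "These subjects will no longer receive the vaccine but will continue with assessments per the study calendar, including collection of study labs". The definition covers allergic or autoimmune reactions of Grade II or higher and any event of Grade III or higher. Pregnancy goes to a medical monitor. Then: "For all other circumstances, the local site PI may determine whether or not a subject needs to be removed from the study".

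On data after removal, 9.2 says: "If a subject withdraws or is withdrawn, they will be asked to complete the Early Termination Questionnaire". Section 7.6 describes that form as recording why a subject left. Section 7.4 has adverse events recorded from consent to the end of study participation, with an exception for possibly related serious events after the study period. Withdrawn subjects are not replaced.

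Safety over 2 years is the primary endpoint (Section 3). Recurrence is compared over 2 years by Fisher's exact test (Section 7.3). Section 8.2 defines a safety population but gives no efficacy analysis set and no rule for subjects whose recurrence status is unknown.

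**The concern.** Stopping injections and ending outcome follow-up are different acts, and the opening list of 9.2 treats them as interchangeable. Two things follow.

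- For serious toxicity, the list permits removal from the study while the stopping rule and 7.2 require continued assessment.
- For milder related reactions, only the permissive wording applies. The less severe event therefore gives weaker protection of the outcome data.

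The possible loss is tied to treatment. The placebo is saline. PepCan contains Candin, and injection-site reactions were the most common adverse events in Phase I. Blinded judgement of relatedness does not equalise arms whose reaction rates differ, so removals would probably be more frequent on PepCan. What could be lost is the 2-year recurrence status (the efficacy outcome) and later adverse events (the primary endpoint). Data never collected cannot be recovered by the choice of test.

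**Working it through.** **Passages side by side.**

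| Event | Opening list, 9.2 | Stopping rules, 9.2, and 7.2 |
|---|---|---|
| Related, serious or dose-limiting | May leave vaccination or the study | Stops vaccine, stays in assessments |
| Related, milder | May leave vaccination or the study | No keep-following rule; local site PI decides |

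**The plan's own figure (Section 8.1).** Inputs: recurrence 80% on placebo and 44% on PepCan, 3:1 allocation, two-sided 5%, 90% power. Pooled rate = (0.80 + 3 × 0.44)/4 = 0.53.

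Placebo n = [1.96 √(0.53 × 0.47 × 4/3) + 1.2816 √(0.80 × 0.20 + 0.44 × 0.56/3)]² / 0.36² = (1.130 + 0.631)² / 0.1296 = 23.9, so 24, with 72 on PepCan. This reproduces the plan (power 0.901). The plan enrols 75 and 25 to allow for about 5% dropout. The withdrawal clause does not alter these numbers.

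**Logical extremes for the PepCan rate.** The removal shares are assumptions. Take a true 33/75 = 44%, with removed subjects dropped from the denominator.

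- 8 removed (about 10%): if all 8 would recur, (33 − 8)/67 = 37.3%; if none would, 33/67 = 49.3%.
- 15 removed (20%): (33 − 15)/60 = 30.0%; 33/60 = 55.0%.

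These are bounds, not predictions. If 8 subjects are removed at random, the chance that all would recur is (33/75)(32/74)…(26/68) ≈ 0.001. The chance that none would is (42/75)(41/74)…(35/68) ≈ 0.007.

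**Type I error of Fisher's exact test, by exact enumeration.** True recurrence is 80% in both arms, with 25 on placebo and 75 on PepCan. A share w of the PepCan arm is removed with recurrence unobserved, and none on placebo. With no removal the error is 0.034.

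If removed subjects have risk r and are dropped, the apparent PepCan rate is (0.80 − w r)/(1 − w). If they stay in the denominator as recurrence-free, it is 0.80 − w r. At w = 20%:

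| Handling of removed subjects | Apparent PepCan rate | Type I error |
|---|---|---|
| Dropped, r = 80% | 0.64/0.80 = 80% | 0.036 |
| Dropped, r = 60% | 0.68/0.80 = 85% | 0.079 |
| Dropped, r = 100% | 0.60/0.80 = 75% | 0.053 |
| Counted recurrence-free, r = 80% | 64% | 0.279 |

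At w = 10% the same four rows give 0.035, 0.047, 0.034 and 0.088.

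**Power.** At 80% against 44%, non-informative loss on PepCan only leaves exact power at 0.85 or more for w up to 30%, against 0.890 with no loss.

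**The case against.** The strongest reply is that 9.2, read through, resolves itself. The specific stopping rule governs serious toxicity, pregnancy has its own route, and the local PI decides the rest. The keep-following rule is silent on milder events, so it cannot contradict the list there. This largely stands. Direct conflict is limited to serious toxicity, and even there the specific rule may be taken to prevail, though sites have to infer that.

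A reader might infer that the clause in effect deletes PepCan outcomes and breaks the randomised comparison. The documents do not support that. The clause says an investigator may act, offers stopping vaccination alone as an alternative, is applied under blinding, and covers both arms.

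A reader might also infer that a large share of the PepCan arm would be removed, because injection-site reactions are common. Phase I points the other way. On a four-injection schedule, 34 subjects received 132 of 34 × 4 = 136 possible injections (97%), with no dose-limiting toxicity and no listed vaccine-related event above grade 2. That experience bears on completing injections, and it gives no support for assuming 10% or 20% removal. It also means that the keep-following rule would protect few subjects, since milder events are what the unrestricted wording covers.

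Finally, non-informative loss with removed subjects dropped leaves type I error near its no-loss value. That is correct, but the plan does not say that removed subjects would be dropped.

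**Conclusion.** The point holds as a gap in outcome follow-up and an inconsistency to be reconciled. Section 9.2 permits off-study removal for vaccine-related toxicity of any grade, and no passage provides for recurrence follow-up, or general adverse-event follow-up, after it.

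The effect ranges from none to large. It depends on three things the documents do not give: how often the clause is used, whether the removed subjects differ in recurrence risk, and how unobserved outcomes are counted. With an assumed 20% removed on PepCan only, type I error runs from 0.036 to 0.279. Dropping removed subjects can push the apparent PepCan rate up or down; counting them as recurrence-free favours PepCan. The 37–49% and 30–55% bands are extremes under assumed removal shares. It is worth correcting because the correction is cheap and the loss cannot be repaired later.

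**What to change.** Reconcile the opening list of 9.2 with the Individual Subject Stopping Rules and 7.2, so that stopping injections and ending outcome follow-up are stated separately. Leave unchanged the reasons for stopping injections, the pregnancy decision, the investigator's best-interest discretion, and the Section 5.5 rule under which recurrence completes participation.

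Add that, unless consent is withdrawn, subjects taken off injections or off study visits before recurrence continue to have recurrence and adverse-event status collected to 2 years, by record review or contact if visits stop. In 8.2, state that they are analysed in their randomised arm, and how any outcome still unknown enters the Fisher comparison.

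The cost is protocol wording and a few extra visits or record reviews, of the kind already planned for subjects with serious toxicity.
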